## Abstract

|                    |  |
|--------------------|--|
| Research Name      | Effects of paravertebral block on postoperative analgesia in children undergoing lateral incision cardiac surgery with cardiopulmonary bypass: a randomized controlled trial (PVB research)  |
| Research Goal      | This study aims to determine whether postoperative PVB has better postoperative analgesic effect, lower complication rate and quicker recovery process compared to local infiltration anesthesia for children undergoing side-incision cardiac surgery with cardiopulmonary bypass.  |
| Research Design    | Single-center, randomized, controlled, double-blinded  |
| Study population   | Children aged 6-14 years who undergo side-incision atrial septal defect repair and/or ventricular septal defect repair surgery with cardiopulmonary bypass   |
| Study intervention | After surgery, patients in the experimental group undergo paravertebral block using drug A, and local infiltration anesthesia using drug B. For the experimental group, drug A is 3mg/kg of 0.375% ropivacaine and drug B is normal saline solution of the same volume. After surgery, patients in the control group undergo paravertebral block using drug A, and local infiltration anesthesia using drug B. For the control group, drug B is 3mg/kg of 0.375% ropivacaine, and drug A is normal saline solution of the same volume.                             |
| Inclusion criteria | (1) Children aged 6-14 years old;
(2) Children who have atrial septal defect or ventricular septal defect scheduled for lateral incision cardiac surgery with cardiopulmonary bypass;
(3) Inform consent signed by the parent or legal guardian.   |
| Exclusion criteria | (1) Patients who were intubated, on mechanical circulatory support, or with intravenous inotropes before surgery;
(2) Emergency surgery or redo cardiac surgery;
(3) Body weight more than 50 kg;
(4) Diagnosed as severe pulmonary hypertension;
(5) Left ventricular ejection fraction less than 45% in most recent echocardiography before surgery;
(6) Allergic to ropivacaine or other regular anesthetics, analgesics or other medications regularly used in the study;
(7) Preoperative platelet counts less than 100*109/L, coagulopathy |

|                   |  |
|-------------------|--|
|                   | or bleeding tendency ;
(8) Preoperatively using antiplatelets or anticoagulants;
(9) Diagnosed with scoliosis or other contraindications for PVB.  |
| Primary outcome   | Total opioid consumption within 24 hours after surgery (ug/kg)   |
| Secondary outcome | (1) FPS-R scores at 6 hours, 12 hours, 18 hours, and 24 hours after surgery

(2) The rate of opioid treatment for remedial analgesia between groups.

(3) The first time of FPS-R $\geq$ 4 postoperatively. (recorded by bedside nurse)

(4) Length of postoperative mechanical ventilation, length of ICU stay and hospital stay.

(5) The rate of postoperative nausea and vomiting (PONV) 24 hours after surgery

(6) The incidence of respiratory depression in the two groups |
| Study period      | 2024.3.11-2024.12.31   |
| Sample size       | 100 (50 cases each for experimental group and control group)   |

## 1. Research Background

Postoperative pain after cardiac surgery is severe, and adequate postoperative analgesia is crucial for quick recovery for cardiac surgery patients. The traditional postoperative analgesia model for cardiac surgery is mainly based on opioids. However, the use of large doses of opioids can lead to delayed postoperative recovery. In recent years, the promotion and application of accelerated recovery surgery theory have led to an overall improvement in medical quality (1, 2). The theory of Enhanced Recovery After Surgery emphasizes postoperative multimodal analgesia to reduce opioid use. Postoperative intravenous analgesia combined with regional anesthesia is one of them, such as combined epidural anesthesia, spinal anesthesia, sacral anesthesia, thoracic paravertebral nerve block (PVB), etc.

However, there are risks associated with epidural anesthesia, spinal anesthesia, or sacral analgesia after cardiac surgery. Cardiac surgery requires systemic blood heparinization, which despite neutralization with protamine, can leave patients more susceptible to serious complications such as epidural hematoma than with other types of surgery. Therefore, new regional blocks such as PVB have gradually emerged in recent years. Compared with epidural block, PVB is easier to operate and can avoid complications

such as epidural abscess, hematoma, general spinal anesthesia, spinal cord, or spinal nerve injury.

An RCT of patients undergoing central sternotomy for cardiac surgery showed that patients who underwent bilateral PVB had the same postoperative pain scores, shorter postoperative ICU length of stay, less nausea and vomiting, and less urinary retention compared to those who underwent epidural blockade (3). Another RCT showed that during side-incision cardiac surgery, patients who underwent unilateral PVB had no significant difference in postoperative pain scores and had lower rates of nerve block failure and nausea compared with patients who underwent epidural blockade. The incidence of complications such as vomiting, urinary retention, and hypotension is also lower (4). However, there are currently no RCT studies in side-incision cardiac surgery comparing postoperative paravertebral blockade with intravenous analgesia alone/incisional local anesthetic infiltration. In thoracic surgery, similar studies have been conducted with positive results (5, 6). An RCT study of PVB for lung surgery showed (6) that compared with simple intravenous analgesia, the PVB group had lower postoperative pain scores and less morphine consumption; while local infiltration analgesia had no significant difference compared with intravenous analgesia alone (5). At present, the number of minimally invasive cardiac surgeries with side incisions is gradually increasing. In order to cooperate with the development of surgery and enhanced recovery process, it is crucial to develop postoperative PVB analgesia technology. This study aims to determine whether postoperative PVB has better postoperative analgesic effect, lower complication rate and faster recovery process compared with simple local infiltration anesthesia for children undergoing side-incision cardiac surgery with cardiopulmonary bypass.

## 2. Research purpose

This study aims to determine whether postoperative PVB has better postoperative analgesic effect, lower complication rate and faster recovery process compared with simple local infiltration anesthesia for children undergoing side-incision cardiopulmonary bypass cardiac surgery.

## 3. Research Method

### 3.1 Overview of experimental design

This study is a single-center, randomized, double-blind trial that aims to determine whether post-operative PVB provides better postoperative analgesia, lower incidence of complications, and faster recovery process compared with simple local infiltration anesthesia for children undergoing side-incision cardiac surgery with cardiopulmonary bypass. This trial will be registered on ClinicalTrials.gov before starting. A detailed statistical analysis plan will be developed before starting data analysis. Results reporting

will strictly follow CONSORT guidelines.

### 3.2 Subject selection

#### 3.2.1 Inclusion criteria

- (1) Children aged 6-14 years old;
- (2) Children who have atrial septal defect or ventricular septal defect scheduled for lateral incision cardiac surgery with cardiopulmonary bypass;
- (3) Inform consent signed by the parent or legal guardian.

#### 3.2.2 Exclusion criteria

- (1) Patients who were intubated, on mechanical circulatory support, or with intravenous inotropes before surgery;
- (2) Emergency surgery or redo cardiac surgery;
- (3) Body weight more than 50 kg;
- (4) Diagnosed as severe pulmonary hypertension;
- (5) Left ventricular ejection fraction less than 45% in most recent echocardiography before surgery;
- (6) Allergic to ropivacaine or other regular anesthetics, analgesics or other medications regularly used in the study;
- (7) Preoperative platelet counts less than 100\*109/L, coagulopathy or bleeding tendency ;
- (8) Preoperatively using antiplatelets or anticoagulants;
- (9) Diagnosed with scoliosis or other contraindications for PVB.

#### 3.2.3 Subject withdrawal criteria and procedures

The researcher may ask the subject to withdraw from the trial at any time during the research process. At the same time, the subject may also spontaneously request to withdraw from the trial at any time. The reasons for withdrawal include but are not limited to: 1) the subject revokes informed consent; 2) the subject is lost to follow-up; 3) the researcher fully assesses the subject from a safety perspective and deems the subject not suitable to continue the trial.

Withdrawal of informed consent means that after obtaining relevant information about the subject's trial, the subject refuses to have further contact with the researcher or his authorized person. The subject should try to inform the researcher in writing that he or she is withdrawing his or her consent for future follow-up. In case of informed consent, the researcher should specify the specific reasons for the subject's withdrawal of informed consent in the case report form (CRF). Subjects may withdraw from the trial at any time at their own request, or may be asked to withdraw from the trial at any time by the investigator, the Data Safety Monitoring Board or the Clinical Events Committee for safety or behavioral reasons, or if the subject is unable to comply with specific trial procedures. In this case, subjects should be encouraged to stay in contact with the investigators and continue to be followed up by telephone and other means during the

remainder of the trial to better assess the safety indicators of the trial. If a subject withdraws from the trial and withdraws informed consent for future disclosures, no further assessments should be conducted and additional data should not be collected, but the investigator may retain and continue to use any data collected before the withdrawal of informed consent.

Loss to follow-up refers to the inability to contact the subject at the end of the trial. No subject should be considered lost to follow-up until the trial is completed. If the subject does not see the doctor as planned, every effort should be made to contact the subject, which can be by phone, email, text message, social media, or if necessary, by letter and/or registered call if necessary. If the subject has died, the date and cause of death should be obtained. If follow-up of this information is not possible, the last known date of survival determined should be reported and recorded on the subject's CRF form.

### 3.3 Intervention or product introduction

Patients in the experimental group received paravertebral block with 3 mg/kg of 0.375% ropivacaine. Paravertebral block is a commonly used regional block technology. Compared with traditional epidural anesthesia, it has the advantages of relatively stable circulation, lower requirements for coagulation function, and lower complication rate. Paravertebral block can be used for all surgeries from the chest to the pubic symphysis. This study used the thoracic paravertebral block. Specific implementation methods of paravertebral block include blind exploration method, nerve stimulator guidance method, ultrasound guidance method, etc. This study adopts ultrasound-guided paravertebral block technology, which enables accurate positioning and reduce the occurrence of complications such as anesthetic injection into blood vessels and pneumothorax.

### 3.4 Research process

#### 3.4.1 Research flow chart

#### 3.4.2 Research implementation (method, content, steps, etc.)

##### 1) Before surgery:

The investigator will conduct a pre-screening process to assess whether potential subjects are suitable for inclusion in this study. After pre-screening, the investigator will conduct a screening process to assess whether the subjects meet the inclusion criteria. Before the process of screening subjects, researchers need to obtain informed consent. Our assessment mainly collects the following information:

- A. Informed consent: When contacting the subject for the first time, the researcher should explain the entire process of the trial to the subject or their legal representative and obtain their informed consent;
- B. Demographic information: gender, date of birth, race, height and weight;
- C. Medical history: Medical history relevant to this study, including primary diagnosis, NYHA classification, diabetes, hypertension, hyperlipidemia, infective endocarditis,

COPD, peripheral vascular disease, cerebrovascular disease, previous cardiac surgery history, smoking history, allergy history and current medications (beta blockers, ACE inhibitors, ARBs, statins, diuretics);

D. Basic vital signs: body temperature, heart rate, blood pressure, oxygen saturation

E. Related examinations: echocardiography, routine blood tests, liver and kidney function tests, and coagulation function tests

2) Intraoperative:

Implementation of intervention: After the operation, patients in the experimental group and the control group were treated with drug A for paravertebral block, and drug B for local infiltration block through the incision. Paravertebral block is performed under ultrasound guidance, and right T4 paravertebral nerve block is performed. It is recommended to use the needle insertion method in the sagittal plane. Use 0.375% ropivacaine at a dosage of 3 mg/kg. The rest of the intraoperative anesthesia protocol is the same as the clinical routine.

Intraoperative anesthesia management: Give anesthetic drugs and perform intraoperative management according to the routine of the anesthesia center.

Intraoperative record information: basic intraoperative information such as type of operation, operation time, etc.

3) After surgery:

Routine postoperative analgesia plan: Children are not routinely given analgesic pumps and other analgesic measures after surgery. The ICU bedside nurse observes the patient's pain condition at any time. When the patient shows any signs of discomfort or pain (such as crying, painful expression, body twisting, etc.), the ICU bedside nurse conducts a FPS-R pain score on the child. If the FPS-R score is  $\geq 4$ , sufentanil 0.05  $\mu$ g/kg/h will be continuously pumped intravenously. If  $0 < \text{FPS-R score} < 4$ , than Non-opioid analgesics will be given.

Postoperative follow-up information: record the total amount of opioids taken by the patient within 24 hours after surgery; FPS-R scores at 6 hours, 12 hours, 18 hours, and 24 hours after surgery; the time when the first FPS-R  $\geq 4$  points after surgery; incidence of nausea and vomiting 24 hours after surgery, the incidence of serious complications such as respiratory depression, postoperative mechanical ventilation time, ICU stay time, postoperative hospital stay.

3.5 Criteria for suspension/termination of studies

The researcher has the right to suspend/terminate this study at any time during the trial. The reasons for suspension/termination include but are not limited to, 1) The incidence and severity of adverse events reported in this study or other similar studies indicate that continuing this trial will be harmful to the subjects. The subjects pose potential health threats; 2) The subjects are not satisfied with the enrollment.

The researcher has the right to replace any research center at any time during the trial.

The reasons for suspending/terminating the research center's continued participation in this study include, but are not limited to, 1) extremely slow recruitment of subjects and insufficient recruitment; 2) poor trial compliance; 3) inaccurate or incomplete data recording; 4) non-compliance with the GCP guidelines of the International Conference on Harmonization (ICH).

### 3.6 Endpoint evaluation

#### 3.6.1 Effectiveness evaluation

1) Primary endpoint: total opioid consumption within 24 hours after surgery (ug/kg)

2) Secondary endpoints: other postoperative analgesic indicators.

A. FPS-R scores at 6 hours, 12 hours, 18 hours, and 24 hours after surgery. (See attachment 1)

B. Rates of postoperative opioid rescue analgesia use in both groups.

C. Time to first postoperative FPS-R  $\geq 4$  points (recorded by bedside nurse)

D. Postoperative mechanical ventilation time, ICU stay time, and postoperative hospitalization time

#### 3.6.2 Safety evaluation

The incidence of vomiting in two groups of children within 24 hours after surgery

The incidence of serious complications including respiratory depression in the two groups of children

### 3.7 Randomization method and blinding method

#### 3.7.1 Blinding

For children who signed informed consent and screened into the group, their baseline information is recorded, and randomization is conducted after entering the operating room. The children are randomly grouped using the block randomization method. After the random numbers are generated by the computer, all the random numbers are coded and sealed into opaque envelopes. The code, that is, the selection number, was written on the outside of the envelope, and the random number was placed inside the envelope. The children were randomly divided into the experimental group (PVB group) and the control group (local infiltration group). This study is blinded to the intraoperative anesthesiologists, patients, data collectors and analysts, and study result evaluators. Before surgery, a pharmacist who is not involved in the follow-up process opens the envelope and prepares medications based on the grouping results. The pharmacist prepares two medications, A and B for each patient. Drug A for patients in the test group is 3 mg/kg of 0.375% ropivacaine, while for patients in the control group, drug A is the same volume of normal saline. Drug B for patients in the control group is 0.375% ropivacaine at 3 mg/kg, and drug B for patients in the test group is the same volume of normal saline. The anesthesiologists all use drug A to perform paravertebral block on the patients, and drug B to perform local infiltration on the patients. The intraoperative anesthesia management plans of the two groups of patients are exactly

the same, so they are blinded. All patients undergo paravertebral block and local infiltration twice, so they are blinded. The anesthesiologists who collect intraoperative and postoperative data do not know the patient grouping information, so they are blinded. The ICU nurse who evaluates the patient's postoperative pain and adds analgesics does not know the patient's group information and is therefore blinded.

Principle of unblinding: If a subject has an adverse event that is suspected to be related to the trial operation and cannot be alleviated by standard clinical treatment methods, for the safety of the subject, emergency unblinding should be carried out. Before the trial begins, each research center will be educated and instructed on the blinding process. If unblinding is necessary, the principal investigator needs to contact the drug dispenser to obtain the trial drug distribution information of the subject, and this unblinding process can only occur when the safety of the subject is threatened. If feasible, before unblinding, it is best for the principal investigator to communicate with members of the trial team to reconfirm the need for urgent unblinding. Once emergency unblinding is carried out, the reason for unblinding must be recorded in detail in the CRF, and the subject is no longer given the trial drug, but the subject can remain in the trial cohort until follow-up is completed.

### 3.7.2 Randomization method

This study is blinded to the anesthesiologists who performed intraoperative management, patients, and postoperative evaluators. The intraoperative anesthesia management plans of the two groups of patients are exactly the same: drug A is used for paravertebral block and drug B is used for local infiltration anesthesia of the surgical incision. Patients and their families are blinded (both the experimental group and the control group received paravertebral block of the back and local infiltration anesthesia of the wound so that family members and other clinicians ostensibly would not know about the children's grouping). The evaluators are blinded (the person conducting the postoperative pain score does not know the children's grouping and the third-party independent evaluation including the central laboratory does not know the children's grouping either).

## 4. Statistical considerations

### 4.1 Sample size estimation

Sample size calculation is based on the primary outcome, total opioid consumption within 24 hours after surgery. Referring to the preliminary test results, the average total opioid consumption within 24 hours after surgery in the traditional low-dose opioid anesthesia group was  $850 \pm 180 \text{ } \mu\text{g/kg MSE}$ . According to previously published literature (12, 13) and the experience of clinical experts, it is assumed that in the PVB group, total opioid consumption within 24 hours after surgery was reduced by an average of 30%,  $255 \text{ } \mu\text{g/kg MSE}$ . At the same time, the combined standard deviation was conservatively estimated to be  $425 \text{ } \mu\text{g/kg MSE}$ . When the significance level of the

statistical test was taken to be one-sided 0.025, the power level was taken to be 80%. hour. According to statistical principles, 45 children need to be enrolled in each group, and the total number of cases in the two groups is 90. Sample size calculation was performed using the PASS software. Taking into account the maximum possible dropout rate of 10% in the study, this trial will eventually enroll 100 children, 50 children in each group.

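### Does the sample size rest on a control mean that does not belong to the infiltration arm?

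*Combined protocol and SAP*

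**What the plan says.** Section 4.1 bases the sample size on 24-hour opioid consumption. From preliminary results, "the average total opioid consumption within 24 hours after surgery in the traditional low-dose opioid anesthesia group was" 850 ± 180 µg/kg MSE. Citing references 12 and 13 and expert experience, "it is assumed that in the PVB group, total opioid consumption within 24 hours after surgery was reduced by an average of 30" per cent, which is 255 µg/kg MSE. Then "the combined standard deviation was conservatively estimated to be" 425. With one-sided 0.025 and 80% power, this gives 45 per group, raised to 50 for 10% dropout.

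The comparison under test is PVB against wound infiltration (Section 2). Section 3.7.1 gives controls ropivacaine by infiltration and saline in the block; the PVB arm has the reverse.

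The Background (Section 1) says of thoracic surgery that "local infiltration analgesia had no significant difference compared with intravenous analgesia alone". It also says that no randomised trial in side-incision cardiac surgery has compared PVB with either intravenous analgesia alone or infiltration.

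**The concern.** Section 4.1 describes the preliminary group by its opioid regimen and does not mention infiltration. It also does not say what PVB was compared with in the sources for the 30%.

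Two sentences elsewhere can be read as hints that the group was not infiltrated. The Background says "The traditional postoperative analgesia model for cardiac surgery is mainly based on opioids". Section 3.4.2, under the intraoperative steps, says "The rest of the intraoperative anesthesia protocol is the same as the clinical routine", which could mean that block and infiltration are both additions to usual care.

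If the 850 came from children without any regional technique, and infiltration reduces opioid use, the control mean would lie below 850. The difference between arms could then be smaller than 255. The trial could miss a real advantage of PVB over infiltration, and readers who see 80% power on record might take a non-significant result as evidence of no advantage.

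**Working it through.** **Inputs.** From Section 4.1: mean 850, preliminary SD 180, reduction 30%, planning SD 425, one-sided 0.025, power 80%, dropout 10%. Section 4.2 tests two-sided at 0.05, which gives the same n. The documents give no opioid-sparing effect of infiltration; it is written f below, and its values are assumptions.

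**1. The plan's own figure.**
- Difference: 0.30 × 850 = 255. Standardised: 255/425 = 0.60.
- Normal approximation: n = 2 × (1.960 + 0.842)² / 0.60² = 43.6, so 44 per arm.
- Two-sample t-test (noncentral t): 44.6, so 45 per arm, as stated. Power is 80.4% at 45 and 84.4% at 50.
- Dropout: 45/0.9 = 50 per arm, 100 in total, as stated.

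**2. If infiltration spares a fraction f.** Control mean = 850 × (1 − f).
- Reading A, PVB mean stays at 850 − 255 = 595: difference = 850 × (0.30 − f).
- Reading B, PVB takes 30% off the infiltration mean: difference = 0.30 × 850 × (1 − f).

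Power with 45 per arm at SD 425:

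| f | A: difference | A: power | B: difference | B: power |
|---|---|---|---|---|
| 0% | 255 | 80.4% | 255 | 80.4% |
| 5% | 212.5 | 65.0% | 242.2 | 76.2% |
| 10% | 170 | 46.7% | 229.5 | 71.7% |
| 15% | 127.5 | 29.1% | 216.8 | 66.7% |

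**3. Dependence on the SD.** The planning SD is 425/180 = 2.4 times the preliminary one.
- At SD 180, reading A, power is 99% at f = 10% and 91% at f = 15%. It stays at or above 80% up to f of about 17%.
- At SD 300, reading A, power stays at or above 80% up to f of about 9%.
- If the SD scales with the control mean (425 is half of 850), reading B stays at 80.4% for every f.

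**4. Misreading of a null result.** The 95% CI half-width with 45 per arm is t(88 df) × SD × √(2/45) = 1.987 × 0.2108 × SD = 0.419 × SD.
- At SD 425 it is 178. A non-significant observed difference between 255 − 178 = 77 and 178 would leave 255 inside the interval.
- f does not enter this calculation. The same window exists when the preliminary group matches the control arm perfectly.
- The window exists only if 2 × 0.419 × SD > 255, that is, if the observed SD exceeds about 304. At SD 300 the half-width is 126 and 255 − 126 = 129, so there is no window. At SD 180 the figures are 75 and 180, again none.

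**5. Share of children given opioid.** Section 3.4.2 says "Children are not routinely given analgesic pumps and other analgesic measures after surgery", and Section 3.6.1 lists as an endpoint "Rates of postoperative opioid rescue analgesia use in both groups". For a non-negative total with mean m and SD s, the share above zero is at least 1/(1 + (s/m)²). This is 95.7% for 850 ± 180 and 80.0% for 850 ± 425. The bound applies to any group with those figures, infiltrated or not, so it does not bear on the comparator.

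**6. The textual hints.** The Background sentence is a general remark on cardiac surgery. The sentence in Section 3.4.2 describes procedures during this trial, not care in the preliminary group. A low-dose opioid label describes opioid dosing and does not exclude infiltration. None of the three settles the question.

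**The case for a change.** The strongest case for acting is that no sentence in the plan says infiltrated children average 850, or that PVB takes 255 off that. The Background finding does not fill the gap: it comes from thoracic surgery, a non-significant difference is not equivalence, and Section 4.1 does not use it. At SD 425 on reading A there is practically no margin, since f above about 0.1% takes power at 45 per arm below 80%. One to three sentences would close the gap without enrolling another child.

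The gap itself stands. The consequence drawn from it does not. The 80% is already tied to stated inputs: 850, an assumed 255 and SD 425. In a trial with only one other arm, the natural reading is that 850 stands for that arm. The 30% is attributed to literature and expert experience, and what those sources compared cannot be judged from these documents.

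Replacement wording would also gain little. Stating 80% power for a difference of 254 at SD 425 with 45 per arm repeats 255, 425 and 45 almost exactly. A rule that calls a result inconclusive according to its confidence interval presumes a difference in means, whereas Section 4.2 moves to a rank sum test for skewed data and specifies no interval.

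**Conclusion.** The concern identifies missing justification, not a fault in the design. Section 4.1 does not describe the regional technique, if any, in its preliminary group. Its arithmetic is right: 45 per arm and 80.4% power from its own inputs.

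The large power losses, such as 47% at f = 10%, need three things together: an infiltration effect absent from the documents, the less favourable reading of the 30%, and the SD of 425 that the plan itself calls conservative. Without the last, power at f = 10% is 99%. The one relevant statement in the documents leans towards little sparing, though it does not establish it.

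A reader can take 850 as the assumed infiltration-arm mean and carry out the plan as written. Writing that assumption down would be tidy, but it would alter neither enrolment, nor the test, nor the result. No change is called for. This would need another look only if the sponsor's preliminary data or cited sources showed a material opioid-sparing effect of infiltration in this surgery.
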